8.6 Treatment After Study Participation

Following participation in the study, subsequent patient care will be decided by their consultant gastroenterologist, according to usual practice.

8.7 Discontinuation of Study Treatment

In line with usual clinical care, cessation or alteration of regimens at any time will be at the discretion of attending clinicians, or the participants themselves. All participants who discontinue from treatment, or who are prescribed alternative treatment, will still attend for follow-up assessments and complete questionnaires, unless they withdraw from the trial (see section 10). Data pertaining to safety will continue to be collected for regulatory reporting purposes and will be included in any safety analysis. The reason for discontinuing study medication will be recorded. Reasons for study treatment discontinuation include:

- Patient decision;
- Severe non-compliance to this protocol as judged by the investigator;
- Safety, including allergic reaction to IMP;
- If the investigator considers that a patient's health will be compromised due to AEs or concomitant illnesses that develop after entering the study;
- Receipt of a restricted concomitant medication after entering the study;
- Pregnancy;
- Overdose;
- Suicidal ideation;
- Flare of disease activity.

Once study medication is permanently discontinued it cannot be restarted as part of the study. Patients should return all unused IMP on cessation of trial treatment. If a participant withdraws from treatment, a Treatment Discontinuation CRF should be completed by the site.

9. ASSESSMENTS AND DATA HANDLING

9.1 Data Collection

Data will be collected for all participants registered to the MODULATE trial. Data will be collected by Remote Data Entry (RDE) on electronic Case Report Forms (eCRFs) managed by the CTRU at the University of Leeds. Access to the live MODULATE database will be provided by the CTRU following site being authorised to open to recruitment; guidance on RDE and completing eCRFs will be provided.

Paper CRFs and participant questionnaires will also be provided for some assessments. Questionnaires completed electronically will be via 1) REDCap electronic patient-reported outcome software 2) an online automated entry system for the CNAQ data http://www.cnaq.com.au (see below). Paper CRFs will be provided electronically by the CTRU at the University of Leeds.

CRFs must only be completed by personnel authorised to do so by the PI, as recorded on the trial-specific authorised personnel log. The original 'wet ink' version of the completed CRFs should be returned to CTRU by fax or Secure File Transfer (SFT). Copies of the completed CRFs should be retained by the site and stored in the investigator site file (or a statement of their location). All data queries, notifications and requests for information should be sent to [contact].

The original copy of the consent form must be filed in the investigator site file and a photocopy faxed or securely emailed using SFT to CTRU.

It is the responsibility of staff at research sites to redact all personal identifiable data, with the exception of the participant consent form, where the participant name and signature must not be redacted. For all other CRFs, patient identifiers will be used to identify the patient as follows; trial number, initials, and date of birth.

9.1.1 Participant Questionnaires – Process Overview

All participants will be asked to complete questionnaires at the following time points:

Baseline – participants must be provided with either a paper questionnaire booklet in the post or a link for the REDCap system via text and/or email to complete the questionnaire online prior to randomisation.

8 weeks – participants can opt to complete the 8-week questionnaire online or on paper. For those choosing the paper questionnaire a booklet containing all the questionnaires will be posted directly to the participant's home address by CTRU.. Participants who chose to complete online assessment will be sent a link to the REDCap system via text and/or email to complete the remaining 8-week questionnaires,

6 months – participants can opt to complete the 6-month questionnaire online or on paper. For those choosing the paper questionnaire this must be completed by the participant when they attend their 6-month face-to-face visit.

Participants who choose to complete online assessments will be sent a link to the REDCap system via text and/or email to complete the 6-month questionnaires. If participants have not completed them by the time they attend the 6-month face-to-face visit, they should complete them on paper during this visit.

9.2 Assessments

9.2.1 Schedule of Events

A tabulated summary of all assessments is provided in Appendix 5

9.2.2 Treatment Arm Specific Assessments – Overview

For full details of the treatment specific assessments please see section 8 and the Schedule of Events. In summary:

Control Group: no additional assessments

Low FODMAP Arm:

- Face-to-Face appointments with the dietitian during week 1 and after week 8 for participants randomised to this arm.
- Telephone call (16 weeks) and face-to-face appointment (24 weeks) with dietitian for responders only. All participants (including non-responders) will also see a research nurse at 24 weeks as per section 9.2.2 below.

Drug Intervention Arms:

- Telephone calls from the research nurse at weeks 1 and 3, and month 3, postrandomisation. Please refer to the treatment specific guidance provided for each individual study drug in section 8 for details.
- Participant diary cards participants to record the number the number of tablets they have taken each day on diary cards from start to completion of study treatment. The diary cards are to be used as participant guidance so participants can monitor their own adherence to medication.

Assessments to be carried out for all patients in all arms are detailed below in section 9.2.3.

9.2.3 Baseline Assessments – All Participants

Prior to randomisation the following baseline information will be collected by a member of the research team for all patients:

- socio-demographic details;
- current medication;
- past medical history and medications;
- duration and extent of UC;
- previous or current psychiatric diagnoses.
- Suicidal ideation

Prior to randomisation all potential participants must complete either a paper baseline questionnaire and assessment booklet sent in the post or an online questionnaire and assessment booklet accessed via REDCap, consisting of:

- Discomfort from loose stools, diarrhoea, urgency, and abdominal pain on the GSRS-IBS [26];
- Disease-specific quality of life via the IBD-Q [27];
- HADS [28];
- CNAQ [34]: nutrient and FODMAP intakes will be quantified via a validated food frequency questionnaire, the Monash University CNAQ. This measures intake of energy, carbohydrate, protein, fat, dietary fibre, total FODMAPs, fructans, GOS, polyols as sorbitol and mannitol, fructose, excess fructose, and lactose.

9.2.2.1 8-week Assessments- All Participants 9.2.2.1.1 Patient Reported Questionnaires

Participants will self-complete a postal or web-based questionnaire, depending on individual preference, at 8 weeks post-randomisation. They will be sent an SMS reminder and an email to prompt completion. If participants are completing paper questionnaires, their research nurse will call them to prompt completion one-week from the date of postage. If questionnaires have not been completed within 1 week of the reminder, a further reminder will be sent 1 week later, and the study team will attempt to contact the participant to collect data for the primary and secondary endpoint over the telephone.

For the low FODMAP arm patients should complete these questionnaires before commencing the reintroduction phase.

Questionnaires will include:

- GSRS-IBS [26];
- IBD-Q [27];
- HADS [28];
- Need for either escalation of medical therapy for UC or surgery;
- CNAQ [34].

9.2.2.1.2 Data Collection from Medical notes

The following data will be collected from the medical notes and recorded on the CRF:

- Confirmed flare of disease activity;
- Any requirement for escalation of UC-related medical therapy;
- Need for surgery.
- Collection of SAEs/SARs/SUSARs/RUSAEs experienced since randomisation;

9.2.2.2 6-month Face-to Face visit- All Participants 9.2.2.2.1 Patient Reported Questionnaires

Participants will self-complete a questionnaire booklet at 6 months post-randomisation. Participants completing questionnaires online will be sent the questionnaire via text message and/or email. Participants completing questionnaires on paper will be sent the questionnaire via post; the research nurse will contact the participants at 6 months to remind them to complete the booklets and return them. They will be sent an SMS reminder and an email to prompt completion. If the questionnaire has not been completed by the time the participant attends the 6-month face-to-face visit, they will be asked to complete it at the visit on paper.

Questionnaires will include:

- GSRS-IBS [26];
- IBD-Q [27];
- Tolerability;
- HADS [28];
- Need for either escalation of medical therapy for UC or surgery;
- CNAQ [34] (low FODMAP arm only).

9.2.2.2.2 Face-to-Face Visit

At 6 months, participants will be invited to a final face-to-face appointment with a research nurse. Prior to this visit a stool sample collection kit should be sent to the participant.

The following assessments/data collection will be undertaken at face-to-face visit:

- Blood for CRP;
- Stool for FC;
- Any requirement for escalation of UC-related medical therapy;

- Need for surgery;
- Confirmed flare of disease activity.
- Dose of study medication for IMP arms
- SAE/SAR/SUSAR/RUSAE check
- Concomitant medications check.

9.2.3 CNAQ

Nutrient and FODMAP intakes will be quantified via a validated food frequency questionnaire. This will be the Monash University Comprehensive Nutrition Assessment Questionnaire, CNAQ). Participants will be provided with a paper version to record quantities of food they habitually consume. This will measure intake of energy, carbohydrate, protein, fat, dietary fibre, total FODMAPs, fructans, GOS, polyols as sorbitol and mannitol, fructose, excess fructose, and lactose. The CNAQ will be participant completed at baseline and week 8 by all participants. The CNAQ will also be completed at week 24 for participants in the low FODMAP arm. The goal is for each participant on the diet to achieve a total FODMAP intake of no more than 12g per day by week 8 during the restriction stage.

9.4 Archiving Trial Data and Documents Held by CTRU

At the end of the trial, all data held by the CTRU and all trial data will then be securely archived, in line with the Sponsor's procedures, for a minimum of 25 years. Data held by the CTRU will be archived in the University of Leeds archive facility and site data and documents will be archived at the participating centres.

Following authorisation from the Sponsor, arrangements for confidential destruction will then be made. If a patient withdraws consent for their data to be used, it will be confidentially destroyed.

9.5 Definition of End of the Trial

The end of the trial is defined as the date of the collection of the last participant's 6-month data collection item.

10. WITHDRAWAL CRITERIA

Withdrawal from trial treatment is separate from withdrawal from the trial/data collection (see section 8.7). The PI, or delegate should make every effort to ensure that the specific wishes of any participant who wishes to withdraw consent for further involvement in the trial are defined and documented, using the withdrawal CRF, in order that the correct processes are followed by the CTRU and site following the withdrawal of consent. The withdrawal CRF should be returned to CTRU within 24 hours of the research team at the site becoming aware. It should be made clear to any participant specifically withdrawing consent for further data collection in a CTIMP that data pertaining to safety will continue to be collected for regulatory reporting purposes and will be included in any safety analysis. Data already collected will be retained.

In addition, the site should make the participant aware of the fact that, if any significant new information becomes available in regard to the treatment they have received in the trial, it may be necessary to contact them in the future.

Patients who withdraw from the trial follow-up would not need to complete further participant questionnaires. Reasons for withdrawal from the follow-up assessments would include:

- Patient decision;
- Lost to follow-up;
- Death.

11. PHARMACOVIGILANCE

11.1 General Definitions

The Medicines for Human Use (Clinical Trials) Regulations 2004 and Amended Regulations 2006 gives the following definitions

Adverse Event

An AE is any untoward medical occurrence (including deterioration of a pre-existing medical condition) in a patient or clinical trial patient administered a trial treatment / procedure, and which does not necessarily have a causal relationship with this treatment and can include:

- Any unintentional, unfavourable clinical sign or symptom (including an abnormal laboratory finding, for example);

- A symptom or disease temporally associated with the use of a medicinal product, whether or not considered related to the medicinal product.

Adverse Reaction (AR)

An AR is any untoward and unintended response to an IMP related to any dose administered. This definition implies a reasonable possibility of a causal relationship, which is supported by facts, evidence, or arguments to suggest a causal relationship. This definition includes medication errors, and uses of the IMP outside what is foreseen in the protocol (i.e. if an AR occurs as a result of a medication error).

Serious Adverse Event / Serious Adverse Reaction (SAR)

A SAE is any untoward medical occurrence or effect that at any dose:

- Results in death;
- Is life-threatening*;
- Requires hospitalisation or prolongation of existing inpatient's hospitalisation**;
- Results in persistent or significant disability or incapacity;
- Is a congenital abnormality or birth defect;
- Other important medical event (IME)***.

* "Life-threatening" in the definition of "serious" refers to an event in which the patient was at risk of death at the time of the event; it does not refer to an event which hypothetically might have caused death if it were more severe.

** "Hospitalisation" means any unexpected admission to a hospital department. It does not usually apply to scheduled admissions that were planned before study inclusion or visits to casualty (without admission).

***IMEs are events that may not be immediately life-threatening or result in death or hospitalisation, but may jeopardise the participant, or may require intervention to prevent one of the other outcomes listed in the definitions above.

Medical judgement should be exercised in deciding whether an AE is serious. These characteristics must be considered at the time of the event, and do not refer to an event that may hypothetically have caused one of the above. Where an SAE is deemed to have been related to an IMP used within the trial, the event is termed a SAR. Any suspected transmission via an IMP of an infectious agent is also considered a SAR.

Suspected Unexpected Serious Adverse Reactions (SUSARs) A SUSAR is a serious adverse drug reaction that also demonstrates the characteristic of being unexpected, the nature, seriousness, severity, or outcome of which is not consistent with the information about the IMP, as set out in the reference safety information (RSI).

Related Unexpected Serious Adverse Event (RUSAE)

A RUSAE is a serious event that is related, in that it occurs from the administration of any of the research procedures, however it was unexpected as the type of event is not listed in the protocol as an expected occurrence. RUSAEs are reportable in the non-CTIMP arms of the trial only.

11.2 MODULATE Operational Definitions

The safety profile of all the IMPs in MODULATE are well known. It is therefore not the intention of this study to collect all AEs. The occurrence of reportable AEs will be self-reported by the participant on the participant questionnaires at 8 weeks and 6 months for patients in all arms. Only the confirmation of occurrence and corresponding severity (mild-noticeable but not preventing normal activities, moderate-restricting some activities, severe- preventing any activities) will be recorded. SAEs, SARs, and SUSARs will be collected for the duration of the trial. The following AEs will be collected:

- Constipation;
- Abdominal pain / bloating (as part of the condition being treated);
- Headache;
- Nausea;
- Vomiting;
- Rectal bleeding:
- Dizziness

- Drowsiness
- Dry mouth
- Insomnia

11.2.1 Adverse Events / Adverse Reactions and Serious Adverse Events / Serious Adverse Reactions

For general definitions of AEs, ARs, SAEs and SARs, please see section 11.1 above.

When determining whether a SAE or SAR is expected or not, please refer to section 4.8 of the current RSI SPC, for the relevant IMP which is provided in the Investigator Site File.

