8.2.4 Amitriptyline Supply and Assessments

Participants will receive an initial 1-month supply of amitriptyline. This should allow for the maximum titration of amitriptyline in this time period. At each telephone call the research nurse should check to make sure there have been no changes to the participant contact details.

Week 1 Telephone Call:

Participants will be called at week 1 by their research nurse to deal with any queries and provide standardised advice about dose titration.

- Information to be collected:
 - Dose of study medication;
 - Toxicity assessment: collection of SAEs/SARs/SUSARs experienced since randomisation;
 - Concomitant medications check;

Week 3 Telephone Call:

Participants will be contacted by their research nurse by telephone at 3 weeks, to confirm the dose reached during titration and to ensure that there are no contraindications to further medication being issued.

- Information to be collected:
 - Dose of study medication;
 - Toxicity assessment: collection of SAEs/SARs/SUSARs experienced since week 1;
 - Concomitant medications check;
 - Suicidal ideation check: If there is any evidence of suicidal ideation, the participant must stop taking amitriptyline, no further amitriptyline should be issued and their GP should be informed of the need for urgent review to assess their mood and mental health;
 - o Confirm participant contact details;
 - Arrange for a further 2 months of trial treatment to be supplied, if appropriate.

Participants will be offered a review with their gastroenterologist (either via telephone or faceto-face) at approximately 1 month, for safety purposes (in relation to taking the study drug), if the research nurse or patient have any queries or concerns.

Month 3 Telephone Call:

A further telephone call from the research nurse will take place just before 3 months, to ensure that there are no contraindications to further medication being used.

- Information to be collected:
 - Dose of study medication;
 - Toxicity assessment: collection of SAEs/SARs/SUSARs experienced since week 8;
 - o Concomitant medications check;
 - Suicidal ideation check: If there is any evidence of suicidal ideation, the participant must stop taking amitriptyline, no further amitriptyline should be issued and their GP should be informed of the need for urgent review to assess their mood and mental health;
 - Confirm participant contact details;
 - Arrange for a final 3 months of trial treatment to be supplied, if appropriate.

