8.2.5 Amitriptyline Toxicity

The most frequent anticipated toxicities of amitriptyline are as follows:

Aggression	Somnolence
Dizziness	Dry mouth
Headache	Constipation
Drowsiness	Nausea

For a full list of toxicities please refer to the latest SPC for amitriptyline.

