11.3 MODULATE Reporting Requirements

All SAEs, SARs, and SUSARs will be collected from time of consent up to 7 days after the last dose of IMP. All SAEs and SUSARs should be reported to the CTRU within 24 hours of the site becoming aware of the event. If sites become aware of any SARs or SUSARs occurring after this active monitoring period, these must still be reported in an expedited manner **up to 90 days after the end of trial**.

The following details will be collected for each SAE:

- Place the SAE started;
- Full details in medical terms with a diagnosis, if possible;
- Duration (date of onset and date of resolution);
- The arm that the patient was randomised to on study;
- Seriousness criteria;
- Causality, in the opinion of the PI or delegate;
- Local opinion on expectedness as defined by the trial supplied RSI, if applicable;
- Action taken with regard to study medication, if applicable;
- Outcome.

In addition to the above the following details will be collected for each SUSAR:

- Relevant medical history;
- Concomitant medications;
- Treatment for SUSAR;
- Relevant diagnostic tests.

To report an SAE or SUSAR please complete an SAE/SUSAR CRF in as much detail as possible, and ensure that the PI or delegate has reviewed the event for causality and expectedness, and has signed the form.

All SAEs and SUSARs will be reviewed by the CI, or designated representative, to confirm causality and expectedness. In the event of a SUSAR, the CTRU will notify the Medicines and Healthcare products Regulatory Agency (MHRA), research ethics committee (REC), and Sponsors office. SUSARS will be reported to the MHRA and REC within the required expedited reporting timelines.

SAE/SUSAR CRF's should be faxed to the CTRU on [name]

All SAEs/SUSARs will be followed-up until resolution or a final outcome has been reached. All follow-up information should be faxed/emailed to the CTRU as soon as it is available.

Please retain the original SAE/SUSAR CRF until the CTRU confirm all information is complete and any resulting queries have been resolved. At this point the original should be posted to the CTRU in real time and a copy retained in the site file.

 Table 1 Summary of safety reporting requirements

Event	Report on trial CRF					
	Drug arms	Non drug arms				
AE	\checkmark	\checkmark				
AE of special interest	\checkmark	\checkmark				
AR	✓	×				
SAE	✓	\checkmark				
SAR	✓	×				
SUSAR	✓	×				
RUSAE	×	\checkmark				

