11.4 Responsibilities

Principal Investigator:

Activities marked with an asterisk (*) must be performed by a medically-trained doctor

• Checking for AEs and ARs when participants attend for treatment / follow-up;

- Using medical judgement in assigning seriousness, causality, and expectedness using the RSI approved for the trial*;
- Ensuring that all SAEs and SARs (including SUSARs) are recorded and reported to the CTRU within 24 hours of becoming aware of the event, and providing further followup information as soon as available. Ensuring that SAEs and SARs (including SUSARs) are chased with CTRU if a record of receipt is not received within 2 working days of initial reporting;

Ensuring that AEs and ARs are recorded and reported to the CTRU in line with the requirements of the protocol.

CI:

- Clinical oversight of the safety of participants participating in the trial, including an ongoing review of the risk / benefit;
- Using medical judgement in assigning seriousness, causality, and expectedness of SAEs where it has not been possible to obtain local medical assessment (this can be delegated to a clinical co-investigator);
- Immediate review of all SUSARs;
- Review of specific SAEs and SARs in accordance with the trial risk assessment and protocol as detailed in the Trial Monitoring Plan;
- Assigning Medical Dictionary for Regulatory Activities or Body System coding to all SAEs and SARs;
- Preparing the clinical sections and final sign off of the Development Safety Update Report (DSUR).

CTRU:

- Central data collection and verification of SAEs, SARs, and SUSARs according to the trial protocol onto a MACRO database;
- Reporting safety information to the CI, delegate, or independent clinical reviewer for the ongoing assessment of the risk / benefit according to the Trial Monitoring Plan;
- Reporting safety information to the independent oversight committees identified for the trial (Data Monitoring and Ethics Committee (DMEC) and / or TSC) according to the Trial Monitoring Plan;
- Expedited reporting of SUSARs to the competent authority (MHRA in UK), main REC, and Sponsor within required timelines;
- Notifying investigators of SUSARs that occur within the trial;
- Checking for (annually) and notifying PIs of updates to the RSI for the trial;
- Preparing standard tables and other relevant information for the DSUR in collaboration with the CI, and ensuring timely submission to the MHRA and Main REC.

Trial Steering Committee:

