13.3.9 Safety Analyses

Routine collection of all AEs and ARs will not take place, due to the well-established safety profile of the study drugs. Rates of constipation and flares of disease activity will be of particular interest. Flares of disease activity will be treated as an AE of special interest and reported on a Flare CRF. Rates of constipation will be collected by participants self-report at week 8 and month 6. Other endpoints related to disease activity (Escalation of Medical

Therapy, Need for Surgery, CRP, and FC) will also be summarised as descriptive statistics and presented by arm

Responsible gastroenterologists will be encouraged to report AEs of special interest and SAEs to the trial team. All AEs, SAEs, and SUSARs will be reported to the DMEC within the relevant time frames, and appropriate action will be taken. Any reported form of self-harm, or suicide will be treated as an IME, whether or not related to taking the trial medication, and reported on an SAE form. Descriptive statistics for all safety data will be summarised by arm.

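### Section 8.2.5 names aggression as a frequent amitriptyline toxicity, but the closed AE list in 11.2 has no item for it, so milder cases cannot be compared with control

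*Protocol*

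**What the plan says.** Section 8.2.5 introduces its list with "The most frequent anticipated toxicities of amitriptyline are as follows" and names aggression, somnolence, dizziness, dry mouth, headache, constipation, drowsiness and nausea. It refers to the product characteristics for the full list.

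Section 11.2 states the collection policy: "It is therefore not the intention of this study to collect all AEs". The reason given is that the safety profile of the drugs is well known. Reportable AEs are self-reported on the 8-week and 6-month questionnaires in all arms, as occurrence and severity (mild, moderate or severe). After "The following AEs will be collected" come ten items: constipation, abdominal pain or bloating, headache, nausea, vomiting, rectal bleeding, dizziness, drowsiness, dry mouth and insomnia.

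Section 13.3.9 repeats the policy: "Routine collection of all AEs and ARs will not take place, due to the well-established safety profile of the study drugs". It also says that descriptive statistics for the safety data will be given by arm. Section 3.3 sets the tolerability and safety of the active treatments, compared with control, as a secondary objective.

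**The concern.** A short AE list is a reasonable choice for established drugs in a pragmatic trial. The difficulty is narrower. The protocol names eight harms as the ones most to be anticipated on amitriptyline, asks every participant about seven of them, and leaves out the eighth without giving a reason. Four of the ten items are not in 8.2.5 at all, so the list was not confined to that section's harms and room was found for others.

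What is at stake is one line of the descriptive safety table. With no item, the report can show serious aggression and aggression that ended treatment. It cannot show how often milder aggression occurred on amitriptyline and on control. In an open trial of a psychoactive drug, that comparison is what would tell a prescriber whether the effect is present at low dose.

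**Working it through.** No power or sample size calculation applies. The check compares the two lists and then looks for any other route.

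**Step 1. Match the lists.** Inputs: the eight terms in 8.2.5 and the ten items in 11.2.

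| Toxicity in 8.2.5 | Item in 11.2 |
|---|---|
| Constipation | Constipation |
| Headache | Headache |
| Nausea | Nausea |
| Dizziness | Dizziness |
| Drowsiness | Drowsiness |
| Somnolence | Drowsiness (same meaning) |
| Dry mouth | Dry mouth |
| Aggression | None |

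Six terms match word for word and one by meaning: 6 + 1 = 7 of 8 covered, 8 − 7 = 1 not covered. Distinct items used: 6. Items with no counterpart in 8.2.5: 10 − 6 = 4 (abdominal pain or bloating, vomiting, rectal bleeding, insomnia).

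**Step 2. Look for another route for non-serious aggression on continued treatment.**

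- Telephone calls at weeks 1 and 3 and month 3 (8.2.4): serious events only, for example "Toxicity assessment: collection of SAEs/SARs/SUSARs experienced since week 1". The 6-month visit (9.2.2.2.2) likewise checks serious events.
- Mood checks: the week 3 and month 3 calls screen for suicidal ideation, and HADS measures anxiety and depression. Neither measures aggression.
- AEs of special interest (11.2.3): constipation and flare. Self-harm or suicide is handled as an important medical event.
- Dose reduction for side effects (8.2.2): the calls record dose, but nothing asks why it changed.
- "Table 1 Summary of safety reporting requirements" (11.3): the AE row is ticked for drug and non-drug arms, the AR row for drug arms only. It is a summary, and 11.2 defines which AEs are reportable, so the AE tick leads back to the ten items. An AR recorded in drug arms alone would give no control comparison.
- Investigator duties (11.4): one bullet asks for AEs and ARs to be checked at attendance, without qualification. The separate reporting bullet reads "Ensuring that AEs and ARs are recorded and reported to the CTRU in line with the requirements of the protocol", which again leads back to 11.2.
- The 6-month questionnaire list (9.2.2.2.1) includes a tolerability element with no content shown; the 8-week list (9.2.2.1.1) does not include one. The Trial Summary assesses tolerability by drop-out due to AEs, constipation and flares.

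**Step 3. What is captured.** Serious aggression is reported as an SAE. Aggression that ends treatment appears through the recorded discontinuation reason (8.7) and drop-out due to AEs.

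**Step 4. Who is not asked.** From 13.1.1, phase 2 has 66 amitriptyline and 132 control participants, each with 2 questionnaires. If amitriptyline goes forward, 13.1.2 gives 66 + 38 = 104 and 132 + 19 = 151 with two arms retained, or 66 + 20 = 86 and 132 + 10 = 142 with one. These are recruitment targets before loss to follow-up. The protocol gives no rate for aggression, so no number of missed events can be calculated.

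**Step 5. After the change.** List length 10 + 1 = 11; coverage of 8.2.5 rises from 7 of 8 to 8 of 8.

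**The case against.** The best defence is that the two sections do different jobs. Section 8.2.5 tells sites what to expect; 11.2 is a deliberately short list for every arm, and nothing obliges it to mirror 8.2.5. A selective policy need not justify each omission. This stands to the extent that there is no formal contradiction. It does not explain why one self-named frequent harm was dropped while four items outside 8.2.5 were included.

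A second defence is that some forms are not shown. The 6-month tolerability element is one. Another is the week 8 toxicity check that Appendix 5 marks as patient-completed for amitriptyline, although its label refers to serious events. An optional clinician review at about one month is also offered. A reader might therefore infer too much by saying that aggression has no route into the data at all. The documents do not support that: the AE tick in Table 1 covers all arms, and the investigator is asked to check for AEs and ARs at attendance, so an individual case could be noted. What they lack is a systematic question, put in the same way to amitriptyline and control participants.

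Third, section 12 says that the low doses reduce the risk of side effects, so aggression may be rare here and 8.2.5 may be too inclusive. The protocol cannot settle this. Trimming 8.2.5 would make the sections agree on paper but would yield no data.

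It is also fair that the main psychiatric hazard in the risk assessment, deliberate overdose or suicide, has its own checks and reporting.

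**Conclusion.** The point holds as a minor gap in safety collection. One of the eight toxicities that the protocol itself calls most frequent has no item in the closed list. Non-serious aggression that does not stop treatment will not be systematically asked about, and its frequency cannot be compared with control as 3.3 asks.

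Three assumptions carry this: that drowsiness covers somnolence; that the ten items are exhaustive for non-serious AEs, as the policy in 11.2 and 13.3.9 indicates; and that the forms not shown contain no aggression question.

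It would be wrong to infer that participant safety is left unmonitored or that the trial's conclusions are at risk. Serious and treatment-ending cases are captured, and neither primary endpoint, the phase 2 p-value threshold nor tolerability measured by drop-out is touched. Nor do the documents show that any event will be missed; they show only that the question is not asked.

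**What to change.** Add aggression to the list in 11.2 and to the 8-week and 6-month questionnaires in all arms, with the existing mild, moderate and severe grading, and summarise it by arm under 13.3.9. Asking all arms is essential, since an item in the amitriptyline arm alone would give no comparison.

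The cost is one extra questionnaire item, one database field and a protocol amendment. No visit, call or additional staff time at site is needed.
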